Subject exposures: Sequential subject study ID numbers will be randomized in 1:1 ratio to one of two experimental groups. Study drugs will be prepared daily by the research pharmacy and labeled only with the subject ID # and “study drug”. The patient, anesthesiologist, obstetricians, and research staff will remain blinded to assignment. All study subjects will receive standard care with prophylactic oxytocin bolus and infusion, as well as second-line uterotronics on an as-needed basis per institutional protocol. (**Appendix 2**)

- Calcium: 1 gram CaCl₂ in total volume 60mL delivered over 10 minutes beginning 2 minutes after fetal delivery.
- Placebo: 60mL sterile saline delivered over 10 minutes beginning 2 minutes after fetal delivery

Outcomes and Measurement: The primary outcome will be quantitative blood loss (QBL) in mL, which is calculated by standardized methodology including volumetric (suction cannister contents after subtracting amniotic fluid volume) and gravimetric (weighing soiled surgical sponges, drapes, and pads) assessment. Secondary outcomes will include the following: uterine tone assessments by the obstetric attending on a validated 10-point numerical rating scale¹⁴ (NRS_{UT}) at study drug initiation 2 minutes after fetal delivery and reassessed every 5 minutes thereafter until fascial closure. Additionally, total oxytocin bolus and infusion doses, second line uterotronics, change in hematocrit from preoperative to postoperative day one values, total intravenous fluids, and a composite outcome indicating hemorrhage morbidity including transfusion during the hospital stay, hysterectomy, uterine artery embolization, intensive care admission, and death will be recorded.

Please see Appendix 3 for forms to be filled out by research staff.

Data Analysis: Analyses will be conducted using R and supervised by a biostatistical consultant from the Stanford Quantitative Sciences unit. Continuous data will be represented using mean (\pm SD) or median (interquartile range) for variables not normally distributed and compared using parametric or non-parametric t-tests as appropriate. Categorical data will be presented using proportions and compared using a chi-square (or Fishers Exact) test. Two-sided p-values less than 0.05 will be considered statistically significant.

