Analysis of Primary Aim: The primary outcome of the study is the difference in quantitative blood loss between the two groups on an intention-to-treat basis. Patients who are found to have non-atomic reasons for blood loss including morbidly adherent placenta, hysterotomy extension, cervical, or vaginal lacerations will be included in primary outcome assessment. The trial is also powered for planned subgroup analysis excluding these cases. In addition, subgroup analyses based upon risk factors for atony including chorioamnionitis, total oxytocin exposure, indication for cesarean, magnesium infusion, and preeclampsia will be performed.

Sample size: Power analysis of the data from our pilot RCT revealed that a sample size of 31 patients per arm will have 90% power to detect a difference of 200mL in quantitative blood loss between groups at the $p<0.05$ significance level. The sample size was increased to 60 patients per arm to allow sufficient power for the planned subgroup analysis excluding patients with non-atomic etiologies of blood loss which may occur in up to 40% of cases. This same sample size will also generate 86% power to detect a rank test difference of 2 points in the ordinal secondary outcome measure of NRS_{UT} . We anticipate signing consent documents with approximately 1200 laboring patients to obtain the 120 subjects who meet enrollment criteria, as most of these patients will have normal spontaneous vaginal delivery, some may later decline to participate, some may develop exclusions such as renal dysfunction, and some may require stat delivery without time to safely administer the study medications in addition to standard care.

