We anticipate a two-compartment mammillary model with an effect site. Calcium is administered into the central compartment, also the site of drug sampling. Calcium is also eliminated from the plasma compartment. Calcium may distribute from the plasma compartment to one or more compartments. Drug effect is mediated by the concentration in a hypothetical "effect site", in this case the uterus¹⁷. The effect site permits modeling of hysteresis between the time course of plasma calcium concentration increase and increase in uterine tone measured in Aim 1. PK modeling will be done in the volume and clearance domain and include the influence (if any) of age, weight, gestational age, pH, starting hematocrit, and blood loss.

Equation 1 is an equation for the sigmoidal PD model. Because the measure of drug effect is the NRS_{UT} is an ordinal measure, it will be dichotomized into 4 categories, 0-3, 4-10, 7-10, and 9-10, and modeled as the probability of being in each category as shown in **Figure 2**. PD models will be estimate p_0 , p_{MAX} , C_{e50} , and γ (the baseline probability of uterine tone X, the maximum probability of uterine tone X, the concentration associated with 50% of the change in probability, and the steepness of the concentration versus probability relationship). The effect of pH and uterotonics including oxytocin, methylergonovine, and carboprost on the PD parameters will be explored.

$$p(NRS_{UT} \leq X) = p_0 + (p_{MAX} - p_0) \frac{Ce^{\lambda}}{Ce^{\gamma} + Ce^{\lambda}}$$

Figure 2. PD models will be estimate p_0 , p_{MAX} , C_{e50} , and γ (the baseline probability of uterine tone X, the maximum probability of uterine tone X, the concentration associated with 50% of the change in probability, and the steepness of the concentration versus probability relationship). The effect of pH and uterotonics including oxytocin, methylergonovine, and carboprost on the PD parameters will be explored.

Equation 1: Pharmacodynamic model for the probability of uterine NRS and calcium concentration

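### Hematocrit change is compared without baseline adjustment: the test is unbiased but never more precise than an adjusted one, and the gain from adjusting runs from nil to moderate

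*Combined protocol and SAP*

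**What the plan says.** Specific Aim 1, Outcomes and Measurement, includes among the secondary outcomes "change in hematocrit from preoperative to postoperative day one values". The Data Analysis paragraph that follows gives one rule for all continuous data: they are "compared using parametric or non-parametric t-tests as appropriate". The significance rule is "Two-sided p-values less than 0.05 will be considered statistically significant".

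No section plans a regression, an analysis of covariance or any other baseline adjustment for an Aim 1 outcome. Covariates appear only in the Aim 2 modelling, where the pharmacokinetic model considers "age, weight, gestational age, pH, starting hematocrit, and blood loss". The preoperative hematocrit thus has two uses already: it is needed to form the change, and it is a candidate covariate in Aim 2.

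Allocation is 1:1, and on size the plan says "The sample size was increased to 60 patients per arm". Power is stated for blood loss and for the uterine tone score. None is stated for hematocrit.

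**The concern.** Subtracting the preoperative value is the same as adjusting for it with a slope fixed at 1. If the true slope of day-one on preoperative hematocrit differs from 1, the subtraction over- or under-corrects, and the mismatch stays in the outcome as noise. Estimating the slope from the same two measurements removes that noise.

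What is at stake is precision on one secondary outcome. The confidence interval for the hematocrit difference may be wider than it need be, and a real difference may be somewhat more likely to be missed.

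**Working it through.** **Inputs from the documents.** 60 patients per arm (Sample size); 1:1 allocation (Subject exposures); two-sided 0.05 and an unadjusted comparison (Data Analysis). The plan gives no power, SD, effect size or correlation for hematocrit, so it has no figure of its own to reproduce here.

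**Assumptions.** Let s0 and s1 be the preoperative and day-one SDs within an arm, k = s1/s0, and r the correlation between the two values. All three are unknown; r is varied from 0.3 to 0.9, and k is set at 0.8, 1 and 1.25.

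**Step 1: direction.**
- Change score: V_c = s0² + s1² − 2·r·s0·s1
- Baseline-adjusted: V_a = s1²·(1 − r²)
- Difference: V_c − V_a = s0² − 2·r·s0·s1 + r²·s1² = (s0 − r·s1)²

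A square cannot be negative. It is zero only when r·s1 = s0, that is, when the slope r·k equals 1. The direction therefore needs no assumption about r or k; only the size does.

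**Step 2: equal SDs (k = 1).** V_c = 2·s²·(1 − r) and V_a = s²·(1 − r²), so V_a/V_c = (1 + r)/2. At r = 0.5 this is 0.75, or 25% less variance. At r = 0.8 it is 0.90, or 10% less.

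**Step 3: power.** Take an effect that the change score detects with 80% power at 60 per arm. With the normal approximation, and Q = V_a/V_c, the adjusted power is Φ((1.960 + 0.842)/√Q − 1.960).
- r = 0.5: 2.802/√0.75 − 1.960 = 1.275, giving 90%.
- r = 0.8: 2.802/√0.90 − 1.960 = 0.993, giving 84%.

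| r (k = 1) | V_a/V_c | Power after adjustment, from 80% |
|---|---|---|
| 0.3 | 0.65 | 94% |
| 0.5 | 0.75 | 90% |
| 0.7 | 0.85 | 86% |
| 0.8 | 0.90 | 84% |
| 0.9 | 0.95 | 82% |

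A simulation of 4,000 trials per setting, fitting both analyses to 60 per arm, gave 80% against 90% at r = 0.5, 79% against 84% at r = 0.7, and 79% against 83% at r = 0.8.

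**Step 4: unequal SDs.** With s0 = 1, V_c = 1 + k² − 2·r·k and V_a = k²·(1 − r²).

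| k | r | Slope r·k | V_c | V_a | V_a/V_c | Power after adjustment, from 80% |
|---|---|---|---|---|---|---|
| 1.25 | 0.5 | 0.625 | 1.3125 | 1.1719 | 0.89 | 84% |
| 1.25 | 0.7 | 0.875 | 0.8125 | 0.7969 | 0.98 | 81% |
| 1.25 | 0.8 | 1.000 | 0.5625 | 0.5625 | 1.00 | 80% |
| 0.8 | 0.5 | 0.400 | 0.8400 | 0.4800 | 0.57 | 96% |
| 0.8 | 0.8 | 0.640 | 0.3600 | 0.2304 | 0.64 | 94% |

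The gain is governed by how far the slope is from 1, and so by r and k together.

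**Step 5: starting power.** The 80% is a reference point, since the plan states none. From 20% power, with r = 0.7 and k = 1, adjustment raises it only to 22.7%.

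**The case against.** The strongest case against acting is that nothing here is an error. Under randomization the change-score comparison is unbiased and keeps its type I error rate. Hematocrit is a secondary outcome with no stated power, and neither the primary result nor the sample size turns on it. If the fall in hematocrit does not depend on the starting value, the slope is 1 and nothing is lost. Varying blood loss between the two samples could widen the day-one SD and push the slope toward 1. All of this stands, and it limits the point to efficiency.

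Three stronger readings are tempting, and the documents do not support them:
- **That a chance preoperative imbalance biases the planned result.** The effect of such an imbalance is already part of the extra variance in Step 1. It is not a second harm.
- **That adjustment guarantees a set gain, such as 5 power points for any correlation up to about 0.7.** Steps 4 and 5 show otherwise: the gain can be zero when the SDs differ, and small when starting power is low or r is high.
- **That hematocrit serves as the laboratory check on measured blood loss.** No section gives it that role. Outcomes and Measurement lists it among several items to be recorded, and the short list of secondary outcomes on the Appendix 3 protocol sheet omits it.

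A further fair objection is that the plan allows a non-parametric comparison, which a plain linear model would drop. The power figures above are for the t-test branch and do not cover the rank-test branch. The fix therefore keeps a rank-based option.

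**Conclusion.** The point holds as a matter of efficiency. The planned comparison is valid, but for its parametric form the variance is never below that of a baseline-adjusted comparison and exceeds it unless the slope is exactly 1. Apart from the one degree of freedom, adjustment has nothing to lose.

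The size cannot be fixed from the documents. Starting from 80% power at 60 per arm, and for r of 0.5 and 0.8, the adjusted power is about 90% and 84% with equal SDs, 84% and 80% with a postoperative SD 1.25 times the preoperative one, and 96% and 94% with a ratio of 0.8. These figures rest on assumed correlations and SD ratios, a common slope in the two arms and the normal approximation.

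This is an optional refinement. It does not question the primary analysis, the sample size or the validity of the hematocrit test. How to handle patients transfused before the day-one sample is a separate matter.

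**What to change.** In the Data Analysis paragraph of Specific Aim 1, state that day-one hematocrit will be analysed by a linear model with treatment arm and preoperative hematocrit as terms, and that the adjusted difference between arms will be reported with its 95% confidence interval. Add that a rank-based version of the same adjusted model will be used if residuals are clearly non-normal, and that the raw change will be kept as a descriptive summary for each arm.

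The cost is one degree of freedom (117 rather than 118 residual degrees of freedom with 120 complete patients: 120 − 3 against 120 − 2), a sentence or two of text and one line of R. No new data are needed. The change should be made before unblinding.

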Appendix 2: Stanford Labor and Delivery protocol for intrapartum cesarean delivery

Monitoring: All patients undergoing intrapartum cesarean delivery are monitored by continuous pulse oximetry, 3-lead EKG, and noninvasive blood pressure oscillometry. Blood pressures are obtained every 1 minutes prior to fetal delivery. For clinically stable patients at the discretion of the anesthesia team, blood pressure frequency may be decreased to every 2.5-5 minutes after fetal delivery.

Antibiotics:

- Patients without antibiotic allergy or chorioamnionitis receive 2 grams intravenous cefazolin (3 grams if >120 kg) prior to incision and 500 mg of intravenous azithromycin over a one-hour infusion for endometritis prophylaxis.
- Patients with a clinical diagnosis of chorioamnionitis instead receive intravenous ampicillin 2g, gentamycin 5 mg/kg over a one-hour infusion, and clindamycin 900 mg intravenously

Neuraxial anesthesia:

- Patients with a labor epidural in situ receive epidural top-up with divided doses of 2% lidocaine with epinephrine 1:200,000 to achieve a T4 dermatomal level to pinprick bilaterally (generally 15-25 mL total volume). 100 mcg epidural fentanyl is added at the discretion of the attending anesthesiologist. All patients receive 3 mg epidural morphine prior to case conclusion for postoperative analgesia.
- Patients without a labor epidural in situ receive a single-shot spinal or combined spinal-epidural anesthetic, with a standard intrathecal medication cocktail of 1.6 mL 0.75% hyperbaric bupivacaine, 15 mcg fentanyl, and 100 mcg morphine.

Uterine tone assessment and uterotonic medications:

- At the time of fetal delivery, 2 units of intravenous oxytocin are administered, and an oxytocin infusion is initiated at 7.5 units/hr
- 2 minutes after fetal delivery, the uterine tone is assessed by palpation of the uterine fundus and rated on a scale from 0-10, with 0 representing a completely atonic uterus and 10 representing a firm and completely contracted uterus. This score is recorded. For uterine tone score <8/10, an additional 2 units oxytocin are administered, and oxytocin infusion increases to 15 units per hour

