- Patient received oxytocin infusion for labor induction or augmentation.
- Patient still wants to participate and has signed consents

Please confirm this patient has NO EXCLUSIONS:

- Patient does not have renal dysfunction with serum Cr>1.0 mg/dL
- Patient does not have any known cardiac conditions
- Patient is not receiving a calcium channel blocker (none in last 24 hours)
- Patient is not receiving digoxin for a maternal or fetal indication
- This is not an emergency in which participation in the study could hinder or delay care

Study drug:

- The syringe contains **60mL saline with 1-gram Calcium Chloride OR 60mL saline placebo**
- Administer via syringe pump and microbore tubing over 10 minutes
 - Program a basic infusion on Alaris pump for basic infusion, **360mL/hr**
 - Attach microbore tubing to injection port closest to the patient
 - Start infusion **2 minutes after fetal delivery** (1 minute after cord clamp)
- Assume that every infusion contains 1 gram of calcium and **discontinue** if concerns for extravasation (arm pain and redness or signs of infiltration), hemodynamic compromise (bradycardia and hypotension most common). Contact [name] via email or cell [contact] for any concerns and document on next page.

PLEASE FILL OUT ALL INFORMATION ON THE NEXT PAGE.

STUDY ID NUMBER (on study drug syringe): _____

USE EPIC COMPUTER CLOCK FOR ALL TIMES

Fetal Delivery and oxytocin 2 unit bolus :

Time: _____

2 minutes after fetal delivery:

• Ask obstetrician to rate uterine tone 0-10: Tone: _____

• Start study drug infusion: Time Started: _____

• *If infusion was paused or stopped* Time paused: _____

Time restarted: _____

7 minutes after fetal delivery:

• Ask obstetrician to rate uterine tone 0-10: Tone: _____

12 minutes after fetal delivery:

• Ask obstetrician to rate uterine tone 0-10: Tone: _____

19 minutes after fetal delivery:

• Ask obstetrician to rate uterine tone 0-10: Tone: _____

Side effects (did the patient experience any of the following possibly related to the study drug? Circle Yes/No)

- Arm or IV site discomfort? YES / NO
- Concern for extravasation? YES / NO
- Heart rate change or arrhythmia? YES / NO Describe: _____
- Hypertension or hypotension YES / NO Describe: _____
- Flushing YES / NO
- Abnormal sensations or tastes YES / NO Describe: _____
- Nausea YES / NO
- Vomiting YES / NO
- Other YES / NO Describe: _____

Was the infusion started exactly 2 minutes after fetal delivery? YES / NO

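### The primary QBL comparison is valid but unadjusted; adding the 2-minute tone score already collected is an optional, cheap precision gain of unknown size

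*Combined protocol and SAP*

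**What the plan says.** Analysis of Primary Aim: "The primary outcome of the study is the difference in quantitative blood loss between the two groups on an intention-to-treat basis". Data Analysis gives the only test for it: continuous outcomes are "compared using parametric or non-parametric t-tests as appropriate", two-sided at 0.05, with the choice tied to normality. No Aim 1 analysis names a covariate. The risk factors under Analysis of Primary Aim are for subgroups, and the covariates under Aim 2 belong to the PK/PD models.

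A tone score is due two minutes after delivery:

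- Appendix 2 makes it routine care: "2 minutes after fetal delivery, the uterine tone is assessed by palpation of the uterine fundus and rated on a scale from 0-10".
- Subject exposures blinds the rater: "The patient, anesthesiologist, obstetricians, and research staff will remain blinded to assignment".
- The Appendix 3 form has "Ask obstetrician to rate uterine tone 0-10: Tone" as the first 2-minute item and "Start study drug infusion: Time Started" as the second.
- Outcomes and Measurement lists tone as a secondary outcome, scored "at study drug initiation 2 minutes after fetal delivery and reassessed every 5 minutes thereafter until fascial closure".

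The Sample size paragraph states that "31 patients per arm will have 90% power to detect a difference of 200mL in quantitative blood loss between groups", raised to 60 per arm so that the subgroup without non-atonic bleeding keeps enough power.

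**The concern.** The score is rated blind, costs nothing extra and is meant to be taken as treatment begins. It could plausibly predict how much a patient bleeds. If it does, an analysis that ignores it gives a wider confidence interval than the collected data allow.

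What is at stake is precision, and power for effects below the design target, such as the 100 mL gap between the pilot medians (850 and 750 mL, Table 1). Recruitment is also tight: Potential difficulties names enrolling 120 patients at one site as the main risk, so precision that needs no further patients has some value. A covariate has to be prespecified to be credible, so the choice belongs in the plan now.

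**Working it through.** **1. SD of QBL (not stated).** Working back from 31 per arm, 90% power and 200 mL at two-sided 0.05:

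- Normal approximation: 200 × √(31/2) / (1.960 + 1.282) ≈ 243 mL.
- Noncentral t: 239 mL, used below.

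As a plausibility check, the pilot IQRs divided by 1.349 give (800 − 600)/1.349 = 148 mL for calcium and (1000 − 650)/1.349 = 259 mL for placebo. Pooled, √((148² + 259²)/2) ≈ 211 mL. SDs of 211 and 259 mL would need 24 and 36 per arm (normal approximation), so 31 is plausible. This check assumes normality. It also assumes that the pilot row, labelled only as blood loss, behaves like QBL.

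**2. Unadjusted, 60 per arm, SD 239.** SE = 239 × √(2/60) = 43.6 mL. Half-width = 1.980 × 43.6 = 86.4 mL. Power is 99.5% for 200 mL and 62.3% for 100 mL.

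**3. Adjusted.** Residual SD = SD × √(1 − r²), with one degree of freedom lost. Equivalent n per arm = 60/(1 − r²). r is not in the document, so it is ranged.

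| r (SD 239) | Residual SD, mL | 95% half-width, mL | Power for 100 mL | Equivalent n per arm |
|---|---|---|---|---|
| unadjusted | 239.0 | 86.4 | 62.3% | 60 |
| 0.2 | 234.2 | 84.7 | 64.1% | 62.5 |
| 0.3 | 228.0 | 82.4 | 66.4% | 65.9 |
| 0.5 | 207.0 | 74.8 | 74.7% | 80.0 |

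**4. Other SDs.** Each list runs unadjusted, then r = 0.2, 0.3, 0.5.

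| SD, mL | Half-width, mL | Power for 100 mL |
|---|---|---|
| 211 | 76, 75, 73, 66 | 73, 75, 77, 84% |
| 259 | 94, 92, 89, 81 | 55, 57, 59, 68% |

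Uncertainty about the SD moves unadjusted power for 100 mL from 73% to 55%, which is more than modest adjustment does.

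**5. At the design difference.** Unadjusted power for 200 mL at SD 211, 239 and 259 is 99.9, 99.5 and 98.7% with 60 per arm. With 36 per arm (60 × 0.6, after excluding 40%) it is 98, 94 and 90%. At SD 239 and 60 per arm, at most 0.5 points remain to be gained.

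**6. Validity and cost.** These come from simulation with 60 per arm, an integer 0–10 tone score, HC2 (heteroscedasticity-robust) standard errors, normal or skewed QBL, and equal or unequal arm SDs. Type I error was 4.7–5.4% adjusted and 4.8–5.4% unadjusted. With normal QBL, SD 239 and r = 0, half-width was 86.6 against 86.2 mL, a cost of 0.4 mL. With 10% of scores missing at random and set to the overall mean, half-width was 85.1, 83.0 and 76.3 mL for r = 0.2, 0.3 and 0.5.

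**7. Skewed QBL.** This is simulated with a gamma distribution of shape 2, SD 239 and a 100 mL location shift. The unadjusted rank test has about 77–79% power. The adjusted model for means has about 63–73% for r from 0.2 to 0.5. Regression of ranked QBL on arm and tone has about 80–86%. Adjustment should therefore keep the outcome scale that the plan would otherwise use.

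**8. Is the score pre-treatment?** Form order puts it before the infusion. Outcomes and Measurement ties it to drug initiation. The form records a clock time for the infusion start but none for the score, so a score taken late could not be identified. Order on the form is the only evidence.

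**The case against.** The strongest reply is that nothing is broken. The test is valid, power at the chosen 200 mL is about 99%, and even the 36-per-arm subgroup has 90–98%. That stands, and it makes the point optional.

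The gain may also be small. A 2-minute score below 8 triggers more oxytocin (Appendix 2). Up to 40% of cases may bleed for non-atonic reasons and stay in the primary analysis. Pilot tone IQRs were narrow (8–9 and 7–9, time point not given). All of these could lower r, and at r = 0.2 the half-width falls by under 2 mL. The 100 mL figure is a gap between pilot medians with P = 0.15, not a design target. These objections also stand.

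A reader might infer that the primary analysis is biased or underpowered. The document does not support this: allocation is randomized, the unadjusted comparison holds its type I error, and the stated target is amply powered. A reader might also infer that a model for means should replace the rank option. Step 7 shows that this can lose power when QBL is skewed. Nor is the open choice between means and ranks evidence for this point, since Data Analysis ties it to normality.

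**Conclusion.** The point holds as an optional improvement. The primary comparison is unadjusted although a blinded candidate baseline score is already collected. At an assumed SD of 239 mL, adjustment narrows the 95% CI half-width by about 2, 4 or 12 mL and adds about 2, 4 or 12 points of power for 100 mL, at r = 0.2, 0.3 or 0.5. At 200 mL the gain is negligible.

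These figures rest on an r that the document does not give, an SD inferred from its sample size statement, and roughly normal QBL. They also require the score to be taken before the infusion starts. The form's order suggests this but does not record it. It would go too far to say either that the score is confirmed as pre-treatment or that it is contaminated.

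**What to change.** Keep the normality-based choice in Data Analysis and prespecify the 2-minute tone score as a covariate in whichever analysis applies:

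- In place of the t-test: linear regression of QBL on arm and tone, with HC2 standard errors.
- In place of the rank test: regression of ranked QBL on arm and tone. Do not demote the rank analysis in favour of a model for means.
- In either case, report the adjusted mean difference in mL with its 95% CI, so that the result can be set against 200 mL. Say which analysis supplies the primary p-value.
- Keep the unadjusted comparison as a sensitivity analysis.
- State that the score is taken before the infusion starts, and add one tick box to the Appendix 3 form to confirm it.
- Handle missing or late scores by one rule that ignores arm, such as the overall mean of both arms combined, so that every randomized patient stays in the analysis.

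The cost is a few lines of SAP text and the tick box, with no new measurement and no change in sample size. The downsides are the extra rule for missing or late scores and little return if r is low.
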